#### Secondary Outcome: Vaccine Willingness at 4 Weeks

At the 4-week survey, participants who had not received an additional dose of the vaccine were asked, "How willing are you to receive another COVID-19 vaccine dose?" with response options: "Very willing", "Somewhat willing", "Not willing", or "Don't know". Only participants who responded 'Very willing' were defined as vaccine willing.

Pre-trial vaccine willingness. After enrollment, but before randomization into an intervention arm, participants were asked, "How willing are you to receive another COVID-19 vaccine dose?" with response options: "Very willing", "Somewhat willing", "Not willing", or "Don't know".

Post-trial vaccine willingness: Immediately after the intervention, participants were asked: "How likely are you to make time to get a vaccine in the next month?" with response options: "Very likely," "Somewhat likely," "Not likely," and "Don't know/not sure." They were also asked:

"Are you planning to make an appointment to get the COVID-19 vaccine in the next month?" with options: "Already made an appointment", "Planning", "Not planning", "Don't know/not sure". These questions were asked again in the 4-week follow-up survey, but only among participants who had not received an additional vaccine dose during that time. For participants with missing follow-up data (N=56), responses from the immediate post-intervention survey were used as imputed values.

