### Statistical Analysis Plan

All statistical analyses were performed blind to study arm allocation. We present frequencies and summaries of characteristics by treatment assignment. Standardized mean differences (SMD) were reported. For post-randomization characters, Chi-squared or Fisher's exact tests were used to compare proportions.

Primary analyses were performed under the intention-to-treat principle, including all participants who underwent randomization. Strict intention-to-treat analysis is hard to achieve for two reasons: missing outcomes for participants and protocol non-adherence. For the primary analysis, we used multiple imputation for those lost to follow-up at some point after randomization (as recommended by the CONSORT statement), which has the benefit of including all randomized participants. As a sensitivity analysis, we assessed loss to follow-up assumptions under (1) multiple imputation and (2) protocol non-adherence (see Appendix).

For the primary outcome, we generated risk ratios using a robust Poisson regression model and generated risk differences. For the secondary outcome of vaccine willingness, we generated risk ratios using a Poisson regression model. The model for the overall effect estimation included the randomization arms and a term for the presence or absence of symptoms of anxiety or depression reported between December 2022 and December 2023. For an Intention to Treat (ITT) analysis of a stratified randomized trial, adjustment is recommended for the stratification variable  on the principle that the analysis should follow the design.

To assess the effect of the intervention according to symptoms of anxiety or depression, we restricted them to subsets with or without symptoms. The stratified models included only randomization arms as the independent variable. Similarly, post-hoc stratification analyses for the primary and secondary outcomes were conducted separately among subsets of participants based on the presence or absence of the post-hoc stratification factors (susceptibility to severe

COVID-19, worry about COVID-19 and pre-trial perceptions of vaccine efficacy). The model included randomization arms and accounted for the presence or absence of symptoms of anxiety or depression.

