Lastly, the validity of an ITT effect estimate requires correct adjustment for selection bias due to differential loss-to-follow-up and missing outcome data. We used multiple imputation for loss-to-follow-up and missing data, hence conducting stratified analyses to assess effect modification rather than relying on interaction terms, as standard interaction testing isn't directly applicable to imputed datasets. Details on imputation methods are included in Appendix C. Methods for sensitivity analyses can be found in Appendix B. A series of sensitivity analyses were conducted to address assumptions related to loss to follow-up and protocol adherence, including complete case analysis, inverse probability weighting, perprotocol analysis for participants fully adhering to the intervention, and multiple imputation for missing outcomes, with consistent results observed across primary and secondary outcomes.

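### Missing 4-week answers from 56 participants are filled with answers given straight after the video; unless the appendices already do so, use those answers as imputation predictors, not substitutes

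*Combined protocol and SAP*

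**What the plan says.** In the Combined protocol and SAP, the section on vaccine willingness at 4 weeks describes two items put to participants straight after the video. One asks "How likely are you to make time to get a vaccine in the next month"; the other asks about planning an appointment over the same horizon. Both were repeated at 4 weeks, but "only among participants who had not received an additional vaccine dose during that time". The rule at issue follows directly: "For participants with missing follow-up data (N=56), responses from the immediate post-intervention survey were used as imputed values".

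The Statistical Analysis Plan describes a different method. Its second paragraph says "For the primary analysis, we used multiple imputation for those lost to follow-up at some point after randomization", and its last paragraph says, without limiting this to any outcome, "We used multiple imputation for loss-to-follow-up and missing data". Multiple imputation also appears as a check. The second paragraph says that, as a sensitivity analysis, "we assessed loss to follow-up assumptions under (1) multiple imputation and (2) protocol non-adherence". The closing list of sensitivity analyses includes "multiple imputation for missing outcomes, with consistent results observed across primary and secondary outcomes".

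On where to look for more, the plan says "Details on imputation methods are included in Appendix C", and it refers to Appendix B for the sensitivity analyses. Neither appendix is in the text available for this review.

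**The concern.** The rule gives each of the 56 one fixed value, taken on the day of the video, in place of a 4-week value. That raises three problems.

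- **Exposure.** The intervention did not end with the video. Reminders worded for each arm followed on days 1 and 3. The immediate answers predate them, so for these participants the filled value leaves out part of what was assigned, and that part differs by arm.
- **Reference period.** Both items look one month ahead. Asked after the video, they cover roughly weeks 0 to 4; asked at follow-up, they cover roughly the month after that.
- **Who the item applies to.** At 4 weeks the items were for people with no new dose. Filling a value for someone whose dose status is unknown treats that person as unvaccinated, while the main analysis multiply imputes those lost to follow-up and may impute a dose for the same person.

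At stake is what a 4-week result on these items estimates, and whether a reader can tell which results rest on carried-forward answers.

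**Working it through.** **Inputs from the document.** 56 participants with missing follow-up data; 1:1:1 allocation (Trial Design); follow-up survey 4 weeks after enrollment (Participants); first enrollment April 15 and first follow-up May 13, 2024 (Trial Design), which is exactly 28 days.

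**Inputs assumed.** The text gives no total sample size, response rates, split of the 56 by arm, or yes/no cut for these four-option items. I take total N = 300, 600, 900 and 1,200, a binary version of an item, and the gaps below. The plan has no figure of its own to reproduce.

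**1. Reference periods.** With a 28-day interval and a 30-day month, the two windows overlap by 30 − 28 = 2 days.

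**2. Filled share.** f = 56/N = 18.7%, 9.3%, 6.2% and 4.7%.

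**3. Shift in the risk difference between arms A and B.** Let g be the immediate rate minus the week-4 rate among those filled.

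shift = f_A × g_A − f_B × g_B

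With equal missingness this is f × (g_A − g_B):

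| Immediate (A v B) | Week 4 (A v B) | g_A − g_B | N=300 | 600 | 900 | 1,200 |
|---|---|---|---|---|---|---|
| 40% v 30% | 20% v 20% | +10 | +1.87 | +0.93 | +0.62 | +0.47 |
| 30% v 30% | 30% v 20% | −10 | −1.87 | −0.93 | −0.62 | −0.47 |
| 40% v 30% | 30% v 20% | 0 | 0 | 0 | 0 | 0 |

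The last four columns are percentage points. Row 1 creates an apparent effect where none exists at week 4, row 2 dilutes a real one, and row 3 does neither.

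**4. Uneven missingness.** If the 56 split 28/14/14 and every arm falls by 10 points, the shift between the first arm and another is (28 − 14)/(N/3) × 10 = 1.40, 0.70, 0.47 and 0.35 points.

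**5. Dose status.** If all 56 lacked dose status and 2%, 5% or 10% had a new dose, then 56 × 0.02, 0.05 and 0.10 = 1.1, 2.8 and 5.6, so about 1, 3 or 6 people should have no value for these items. If some of the 56 reported no dose and only skipped the items, the numbers are smaller.

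**6. Interval width.** Take row 1 at N = 300, with 100 per arm and 56/3 = 18.67 filled.

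- Variance of the filled estimate: (81.33 × 0.16 + 18.67 × 0.24)/100² + (81.33 × 0.16 + 18.67 × 0.21)/100² = 0.003443, a standard error of 5.87 points.
- Usual formula on the filled rates, 23.73% and 21.87%: (0.2373 × 0.7627 + 0.2187 × 0.7813)/100 = 0.003519, a standard error of 5.93 points.

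The two agree closely. The reported precision fits the filled quantity; the difficulty is that this is not the week-4 quantity.

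**The case against.** The best defence is that no stated analysis is shown to be affected. The primary outcome is a reported dose, the secondary outcome is 'Very willing' on a different question, and the models in the Statistical Analysis Plan are for those two. No visible model or cut-point exists for the 'make time' and 'planning' items. This stands, and it limits the point to wherever these items are in fact analysed. They are nonetheless listed under the secondary outcome, so a reader needs to know how their 4-week values arose.

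Second, Appendices B and C may settle the matter. This also stands, and the fix is conditional on them. The visible sentence, however, presents the immediate answers as the imputed values, not as inputs to a model.

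Third, complete-case, weighted and multiple-imputation analyses are reported as consistent. That is some reassurance, but the sentence speaks of primary and secondary outcomes and does not say that these two items were covered.

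Fourth, the text does not say whether the 56 missed the whole survey or only some items. Those who reported no dose and skipped the items create no conflict. A literal reading of the primary-outcome definition could also class anyone without a 'yes' as unvaccinated, though that fits poorly with multiply imputing those lost to follow-up.

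A reader might infer that the fill entered the 'Very willing' or primary outcome. The documents do not support that. As described, the general willingness question was asked before randomization and at 4 weeks, not straight after the video, so there is no same-item answer to carry forward. A reader might also infer that a single fill makes the intervals falsely narrow for what they estimate; the last step of the working gives no support for that.

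**Conclusion.** The point holds in limited form. The plan substitutes an immediate answer for a missing 4-week answer in 56 people. The substitute precedes part of the arm-specific intervention and refers to a different month. For those with unknown dose status, it also rests on a presumption that the main imputation does not share. The boundary with multiple imputation, and whether multiple imputation is the main method or the check, is unstated in the visible text.

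The bias cannot be signed and is probably modest: about 1.9 points at an assumed N of 300, falling to about 0.5 at 1,200, if the change to week 4 differs by 10 points between arms. It is zero if change and missingness are both equal across arms, or if answers do not change. Everything beyond the count of 56 in that range is assumed. The change is worth making because the better method is already in the plan, not because any reported result is shown to be wrong. Confidence is medium, since both appendices are unseen.

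**What to change.** First check Appendix C for the imputation model and Appendix B for the coverage of the sensitivity analyses. If the immediate answers already enter as predictors, only the sentence under the secondary outcome needs correcting.

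Otherwise, wherever the 4-week 'make time' and 'planning' items are analysed:

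- Replace the single fill with the multiple imputation already in use. Include arm, symptom stratum, pre-trial willingness and the immediate answers as predictors, and pool by Rubin's rules.
- Where vaccination status is missing, impute it first, so that the items apply only to those observed or imputed as unvaccinated.
- Keep the carry-forward only as a labelled sensitivity analysis.
- In the secondary-outcome section and the Statistical Analysis Plan, state which items and analyses used carried values, how the 56 split by arm, and which method is the main one.

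No new data are needed. The cost is an extension of the imputation to two items and a re-run. Intervals would probably be slightly wider, by an amount not established for this procedure, and the analysed subset would vary between imputations, which should be described. Because the plan already reports results, the re-run must be labelled as a later change and shown beside the existing analysis.

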#### Post-hoc Stratification Variables

Post-hoc stratification analyses were performed to assess differences in primary and secondary outcomes based on susceptibility to severe COVID-19, worry about COVID-19, and pre-trial perceptions of vaccine efficacy. Further details regarding the measurement of these stratification variables were provided in Appendix A.

### Statistical Analysis Plan

All statistical analyses were performed blind to study arm allocation. We present frequencies and summaries of characteristics by treatment assignment. Standardized mean differences (SMD) were reported. For post-randomization characters, Chi-squared or Fisher's exact tests were used to compare proportions.

Primary analyses were performed under the intention-to-treat principle, including all participants who underwent randomization. Strict intention-to-treat analysis is hard to achieve for two reasons: missing outcomes for participants and protocol non-adherence. For the primary analysis, we used multiple imputation for those lost to follow-up at some point after randomization (as recommended by the CONSORT statement), which has the benefit of including all randomized participants. As a sensitivity analysis, we assessed loss to follow-up assumptions under (1) multiple imputation and (2) protocol non-adherence (see Appendix).

For the primary outcome, we generated risk ratios using a robust Poisson regression model and generated risk differences. For the secondary outcome of vaccine willingness, we generated risk ratios using a Poisson regression model. The model for the overall effect estimation included the randomization arms and a term for the presence or absence of symptoms of anxiety or depression reported between December 2022 and December 2023. For an Intention to Treat (ITT) analysis of a stratified randomized trial, adjustment is recommended for the stratification variable  on the principle that the analysis should follow the design.

To assess the effect of the intervention according to symptoms of anxiety or depression, we restricted them to subsets with or without symptoms. The stratified models included only randomization arms as the independent variable. Similarly, post-hoc stratification analyses for the primary and secondary outcomes were conducted separately among subsets of participants based on the presence or absence of the post-hoc stratification factors (susceptibility to severe

COVID-19, worry about COVID-19 and pre-trial perceptions of vaccine efficacy). The model included randomization arms and accounted for the presence or absence of symptoms of anxiety or depression.

Lastly, the validity of an ITT effect estimate requires correct adjustment for selection bias due to differential loss-to-follow-up and missing outcome data. We used multiple imputation for loss-to-follow-up and missing data, hence conducting stratified analyses to assess effect modification rather than relying on interaction terms, as standard interaction testing isn't directly applicable to imputed datasets. Details on imputation methods are included in Appendix C. Methods for sensitivity analyses can be found in Appendix B. A series of sensitivity analyses were conducted to address assumptions related to loss to follow-up and protocol adherence, including complete case analysis, inverse probability weighting, perprotocol analysis for participants fully adhering to the intervention, and multiple imputation for missing outcomes, with consistent results observed across primary and secondary outcomes.

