#### Primary Outcome: Receipt of COVID-19 Vaccine Dose at 4 Weeks

At the 4-week survey, participants were asked, "Have you received a COVID-19 vaccine dose since {date of intervention}?" Participants who responded "yes" were considered vaccinated; otherwise, they were not.

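### The missing-data checks named in the SAP repeat multiple imputation without a stated difference, and none is described as allowing non-response to depend on the unseen outcome, so their agreement does not show robustness to such loss.

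*Combined protocol and SAP*

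**What the plan says.** The Statistical Analysis Plan section names its primary method: "For the primary analysis, we used multiple imputation for those lost to follow-up at some point after randomization". It then describes the check on that method: "As a sensitivity analysis, we assessed loss to follow-up assumptions under (1) multiple imputation and (2) protocol non-adherence". Later in the same section a longer list of sensitivity analyses is given, "including complete case analysis, inverse probability weighting, perprotocol analysis for participants fully adhering to the intervention, and multiple imputation for missing outcomes", and the outcome of the exercise is reported as "with consistent results observed across primary and secondary outcomes". The section also sets its own standard: "the validity of an ITT effect estimate requires correct adjustment for selection bias due to differential loss-to-follow-up and missing outcome data".

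Imputation details are referred to Appendix C and sensitivity methods to Appendix B. Neither is in the document supplied. The only count of missing follow-up is under the secondary outcome: "For participants with missing follow-up data (N=56), responses from the immediate post-intervention survey were used as imputed values". No split by arm or stratum is given, and neither is the total number randomized.

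**The concern.** A sensitivity analysis for missing data should vary the assumption on which the primary analysis depends. Here one of the named checks carries the same name as the primary method, and the text gives no reason to think it varies anything. The remaining missing-data checks change how the adjustment is made, and which covariates enter it. In their usual forms they do not change the assumption that, within arm and covariate levels, people who skipped the 4-week survey had the same uptake as those who answered.

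The design makes a departure from that assumption conceivable. The primary outcome is self-reported in the same survey whose non-completion creates the missing value. Participants knew their assignment, and the reminders were tailored to each arm. Willingness to answer could therefore relate both to vaccination and to arm. If it did, the risk ratio for each video against standard messaging would be biased in the primary analysis and in the named checks alike, and their agreement would give no warning.

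**Working it through.** The plan states no sample size, uptake rate or effect estimate, so there is no figure of its own to reproduce. The check is first a reading of the text, then two illustrations on assumed inputs.

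**Step 1: what each named check varies**

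| Analysis | Role in the plan | Assumption about non-response (standard form) |
|---|---|---|
| Multiple imputation | Primary | Unrelated to outcome given the variables in the imputation model |
| Multiple imputation | Sensitivity | No difference from the primary stated |
| Complete case | Sensitivity | Unrelated to outcome given arm and model covariates |
| Inverse probability weighting | Sensitivity | Unrelated to outcome given the variables in the weight model |
| Per-protocol | Sensitivity | Concerns adherence, not non-response |

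No delta adjustment, tipping point or best/worst-case analysis is named.

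**Step 2: can these methods agree and all be wrong?**

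One simulated data set of 1,000,000 participants in two arms was used. All inputs are assumed. Uptake was 8% in one stratum and 6.4% in the other, with no arm effect. Unvaccinated participants were missing at 8% or 12% by stratum. Vaccinated participants were never missing in the active arm, and were missing three times as often as unvaccinated ones in the control arm. About 10% were missing overall.

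- Full data: RR 1.02
- Complete case: RR 1.41
- Weighting by arm and stratum: RR 1.41
- Multiple imputation by arm and stratum: RR 1.41

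The mechanism is deliberately strong. The result shows only that agreement among the three is not evidence against it.

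**Step 3: how far could 56 missing outcomes move the risk ratio?**

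Assumptions: the 56 also lack the primary outcome, they are split equally over three equal arms, and the RR is 1.00 in responders. The missing fraction per arm is f = (56/3)/(N/3) = 56/N. If responders have uptake p and non-responders have k times p, the arm risk is p[(1 − f) + kf]. Writing kA for the active arm and kC for control:

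RR = [(1 − f) + kA·f] / [(1 − f) + kC·f]

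The uptake p cancels, so none need be assumed.

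| N (assumed) | f | kA=0, kC=1: 1 − f | kA=1, kC=3: 1/(1 + 2f) | kA=1, kC=0: 1/(1 − f) | kA=3, kC=1: 1 + 2f | kA=kC=0 |
|---|---|---|---|---|---|---|
| 300 | 0.187 | 0.81 | 0.73 | 1.23 | 1.37 | 1.00 |
| 500 | 0.112 | 0.89 | 0.82 | 1.13 | 1.22 | 1.00 |
| 800 | 0.070 | 0.93 | 0.88 | 1.08 | 1.14 | 1.00 |
| 1200 | 0.047 | 0.95 | 0.91 | 1.05 | 1.09 | 1.00 |

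For milder departures, take 19 missing in one active arm and control non-responders at the responder rate. Half the responder rate gives 1 − 0.5 × 19/100 = 0.905 at N=300 and 1 − 0.5 × 19/300 = 0.97 at N=900. Double the rate gives 1 + 19/100 = 1.19 and 1 + 19/300 = 1.06.

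**The case against.** The case for the plan has four parts.

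- **The comparison is a real test.** Setting multiple imputation beside weighting and complete case shows whether the result depends on the covariates used or on the adjustment method. A reader might infer from the duplication that robustness was not tested at all. That goes too far, and this defence stands in full.
- **The appendices are not in view.** A reader might infer that the same imputation was run twice, or that no analysis allows outcome-dependent loss. The text shows a repeated name, not a repeated model. Assessing loss-to-follow-up assumptions under multiple imputation could even mean varying them within it. The list is introduced as non-exhaustive, and that the primary imputation is a standard missing-at-random model is itself an inference. This also stands, and it is why the repeated imputation should be explained before anyone removes it. It does not answer the point that the body, as written, gives the reader no difference between check and primary.
- **There is no evidence that loss differed by arm.** All arms saw one-minute videos from one production process and received two reminders. This is fair: the mechanism is conceivable, not shown. But no missing counts by arm are given either, so the text offers nothing to set it aside.
- **The sizes are assumed.** N and the arm split are unknown, the direction could be either, and balanced loss with all non-responders unvaccinated changes nothing. This is correct. It means that only shifts differing by arm are informative.

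**Conclusion.** The point holds in a limited form. Among the analyses named in the body, multiple imputation repeats the primary method with no stated difference, and the other missing-data checks in their standard forms rest on the same kind of assumption. The reported consistency supports robustness to covariates and adjustment method. It does not support robustness to outcome-dependent loss that differs by arm, and the body should not be read as if it did.

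The possible size runs from small to material. Under an equal split and no effect in responders, the first two scenarios give 0.81 to 0.95 and 0.73 to 0.91 as N goes from 300 to 1200, with shifts above 1.00 when the roles are reversed. These figures rest on an assumed N, an assumed split, and the 56 applying to the primary outcome.

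A reader might go on to infer that the trial's estimates are biased or that a conclusion would change. The documents give no estimate, interval or arm-level missingness, so neither can be said. This is an inexpensive improvement to the analysis, not a demonstrated error in the result.

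**What to change.** 1. State in the Statistical Analysis Plan how the sensitivity imputation differs from the primary one. Remove it from the list only if the two are the same.
2. Report the number of missing primary outcomes by arm and by anxiety/depression stratum.
3. Unless Appendix B already contains one, add a delta-adjusted (pattern-mixture) multiple imputation. Shift the log-odds of vaccination for non-responders separately in each arm, in both directions, over a range that is justified in the text. Include all non-responders unvaccinated as one reference case. Report the tipping point for each video against standard messaging. Follow-up is complete and results are already described, so label the analysis post hoc.
4. Keep complete case and weighting as checks of method and covariates, and limit the consistency statement to the assumptions actually varied.
5. Say how the imputation relates to the carry-forward of immediate post-intervention answers for the 56 participants.

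The cost is some rewording and a small amount of analysis. Binary values already imputed cannot have their log-odds shifted, so they must be redrawn from the imputation model. The robustness statement may become weaker as a result.

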### **Study Protocol**

#### Trial Design

In a 3-arm, parallel-group, assessor-blinded, stratified-randomized trial, participants were enrolled based on the following eligibility criteria: aged 18 years or older, having received at least one dose of the COVID-19 vaccine but no doses since September 11, 2023, and no SARS-CoV-2 infection in the three months prior to the study start. We focused on individuals with at least one prior dose—the "moveable middle"—who show some willingness to vaccinate but remain hesitant about additional doses and may be more responsive to a brief video intervention than the unvaccinated. Our team's prior research informed the trial design, and identified safety and efficacy as their main concerns.

Eligible individuals were randomly allocated to one of three interventions: 1) attitudinal inoculation, 2) CBT-kernels or 3) standard public health messaging. Recruitment and randomization started on April 15, 2024 and continued on a rolling basis until May 02, 2024. Outcome assessment at 4-week follow-up started on May 13, 2024 and was completed by June 13, 2024. After consenting, enrolled participants were randomly assigned to one of three arms at a ratio of 1:1:1. Each arm was also stratified by presence or absence of moderate to severe anxiety or depression symptoms, defined by scoring  $\geq$ 10 in the Patient Health Questionnaire-8 or GAD-7 at any point between December 2022 and December 2023.

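### Robust variance is named for the primary outcome but not for binary vaccine willingness; followed as written, the willingness intervals are too wide and the tests conservative

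*Combined protocol and SAP*

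**What the plan says.** Two adjacent sentences in the Statistical Analysis Plan set out the models. For vaccination: "For the primary outcome, we generated risk ratios using a robust Poisson regression model and generated risk differences". For willingness: "For the secondary outcome of vaccine willingness, we generated risk ratios using a Poisson regression model". No other part of the supplied text gives willingness a robust, sandwich or bootstrap variance.

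The Measures section makes willingness a yes/no variable: "Only participants who responded 'Very willing' were defined as vaccine willing".

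The covariates are stated once: "The model for the overall effect estimation included the randomization arms and a term for the presence or absence of symptoms of anxiety or depression". Within the two symptom strata the models contain arm only. The willingness analysis is also repeated in post-hoc subsets: "post-hoc stratification analyses for the primary and secondary outcomes were conducted separately among subsets of participants". On missing data the plan says: "We used multiple imputation for loss-to-follow-up and missing data". It refers to Appendix B for sensitivity methods and Appendix C for imputation; neither is in the supplied text.

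**The concern.** Poisson regression gives a valid risk ratio for a binary outcome, but its default standard error does not fit one. The model sets the variance equal to the mean, p, when the variance of a binary outcome is p(1-p). Sandwich variance is the usual remedy, and the plan names it for the primary outcome. Read literally, the willingness model lacks it.

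The error is conservative. Confidence intervals cover more than 95% of the time, p-values are too large, and a real effect of a video on willingness could be reported as null. This applies to the overall, symptom-stratified and post-hoc analyses. It matters most in the subsets, which have the least information to spare and which the plan relies on, in place of interaction terms, to judge effect modification. If robust variance was in fact used, the text misdescribes the analysis, and anyone repeating it would get different intervals.

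**Working it through.** **Inputs from the documents.** Binary outcome; log-link Poisson model; three arms ("enrolled participants were randomly assigned to one of three arms at a ratio of 1:1:1"); arm plus symptom stratum as covariates; multiple imputation. The supplied text gives no sample size, significance level, power or willingness rate, so there is no stated figure to reproduce.

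**Assumptions.** Willingness rate p from 5% to 40%, similar in the two arms compared; two-sided 5% test; 80% power under robust errors as the benchmark.

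**Step 1: variance of the log risk ratio, arm 1 against arm 0.**

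- Ordinary Poisson: 1/(n1·p1) + 1/(n0·p0)
- Binomial, which the sandwich estimates in large samples: (1-p1)/(n1·p1) + (1-p0)/(n0·p0)

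With a common risk p, the ratio of standard errors is r = 1/sqrt(1-p). At p = 0.20, r = 1/sqrt(0.80) = 1.118.

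**Step 2: consequences.**

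- Actual alpha = 2·(1 - Φ(1.96·r)). At p = 0.20: 2·(1 - Φ(2.191)) = 2.8%.
- Power = Φ(2.80 - 1.96·r), where 2.80 = 1.96 + 0.84. At p = 0.20: Φ(0.610) = 72.9%.

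**Step 3: multiple imputation.** Only the within-imputation variance is inflated. If a share L of the correct pooled variance lies between imputations, the ratio becomes sqrt((1-L)/(1-p) + L). With L = 0.20 (assumed) and p = 0.20, this is sqrt(0.80/0.80 + 0.20) = 1.095.

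| Assumed p | SE ratio | Actual alpha | Power | SE ratio, L = 0.20 | Power, L = 0.20 |
|---|---|---|---|---|---|
| 5% | 1.026 | 4.4% | 78.5% | 1.021 | 78.8% |
| 10% | 1.054 | 3.9% | 76.9% | 1.044 | 77.5% |
| 20% | 1.118 | 2.8% | 72.9% | 1.095 | 74.4% |
| 30% | 1.195 | 1.9% | 67.7% | 1.159 | 70.2% |
| 40% | 1.291 | 1.1% | 60.7% | 1.238 | 64.6% |

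**Step 4: simulation of the plan's overall model.** Three equal arms plus a symptom term, no true effect, no imputation, about 1,500 runs per setting, with 100, 200 or 300 per arm (assumed).

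- At p = 20%: mean SE ratio 1.12; test size 2.1% to 3.1% with model-based variance, 4.2% to 4.9% with robust.
- At p = 30%: mean SE ratio 1.20; test size 1.8% to 2.0% model-based, 4.6% to 4.8% robust.
- At p = 5% with 100 per arm (about five events each): test size 1.2% model-based, 1.8% robust. With so few events neither test is near 5%, so the choice of variance is not the main issue there.

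**Step 5: one worked comparison, assumed counts 40/200 and 60/200.** The risk ratio is 1.50 either way.

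- Ordinary Poisson: variance 1/40 + 1/60 = 0.0417, SE 0.204, 95% CI 1.01 to 2.24, p = 0.047.
- Robust: variance 0.80/40 + 0.70/60 = 0.0317, SE 0.178, 95% CI 1.06 to 2.13, p = 0.023.

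**The case against.** The strongest reply is that the defect is inferred from one missing adjective. The outcome sentences are adjacent, the next speaks of a single overall model, and the post-hoc paragraph treats both outcomes together, so the authors may simply not have repeated the word. Appendices B and C might also name the estimator. This stands as a reason not to claim that the wrong variance was used. It does not rescue the text: the single-model sentence describes covariates, not variance, and the sentence on willingness, taken at its word, specifies the wrong standard error.

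The size rests on an assumed rate. Participants are described as hesitant, only the top response counts, and the question goes only to those still unvaccinated at four weeks, so a low rate is quite possible. At 5% to 10% the excess is only 3% to 5%. That stands too.

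The Measures section also fills missing follow-up (N=56) with responses from the immediate post-intervention survey. If that reached the willingness outcome, treating filled values as observed could narrow intervals, offset some of the excess and make the imputation columns above inapplicable. The text ties it most directly to the likelihood and appointment questions, and it would not correct the variance assumption in any case.

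Finally, the plan reports sensitivity analyses "with consistent results observed across primary and secondary outcomes". That statement says nothing about which variance was used, so it neither supports nor answers the point.

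**Conclusion.** The point holds for the plan as written: an ordinary Poisson model for a binary outcome overstates the standard error at any rate above zero. The direction follows from algebra and was confirmed by simulation. The size depends on the willingness rate, which the documents do not give. It is small below about 10% and material from about 20%, where the excess is 12% before imputation, or 10% if a fifth of the pooled variance lies between imputations. What was actually run cannot be settled from the supplied text, so confidence is medium. The primary outcome and all risk ratio point estimates are untouched, and there is no excess of false positives. It should be corrected, but it does not threaten the trial's main conclusion.

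**What to change.** Check the analysis code or output to see which variance was used for willingness. The analyses are already reported as done, so this is a check of fact.

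- If it was robust, amend the sentence to say that willingness risk ratios came from a robust Poisson regression model, and state that this covers the overall, symptom-stratified and post-hoc models. The cost is one word and a clause.
- If it was not, refit those models with sandwich variance within each imputed dataset, pool, and report the revised intervals with a note that they changed and why. This is a modest rerun with no new data, and the risk ratios will not move.

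The one drawback is that in sparse subsets an uncorrected sandwich variance can be too small, so a small-sample correction may be needed there and should be named if used.
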